### 3. Abstract:

*Cutibacterium acnes* has been the focus of much recent shoulder literature, as it has been found to be both a common cause of periprosthetic joint infection as well as a common contaminant in shoulder surgery. Standard skin preparations have been found to be ineffective at eradicating *C. acnes* colonization on the skin and deep dermis of patients undergoing surgery. Recent literature has shown that skin preparation with 3% hydrogen peroxide solution is effective for decreasing the rate of cultures positive for *C. acnes* in both dermal and deep cultures; however, a positive rate of 10%-17% has still been reported despite this skin preparation. The current theory is that standard skin preparation does not remove *C. acnes* from the deep dermis which subsequently contaminates the deep tissue. We hypothesize that application of 3% hydrogen peroxide to the deep dermal layer immediately following the skin incision will even further decrease the rate of *C. acnes* contamination during surgery.

### 4. Background and Significance:

Over 50,000 people in the United States have shoulder replacement surgery each year. Of these, it is reported that 0.4%-2.9% of anatomic total shoulder arthroplasties (aTSA) and 1-10% of reverse shoulder arthroplasties (rTSA) are complicated by periprosthetic joint infection (PJI).

*Cutibacterium Acnes* (*C. acnes*), an indolent organism found on the skin and in the sebaceous glands around the shoulder and back, makes the diagnosis of shoulder PJI particularly challenging. Multiple studies have shown that *C. acnes* can be isolated from deep cultures in up to 40% of patients without prior surgery undergoing primary total shoulder arthroplasty, although whether this indicates actual colonization of the joint or contamination is an area

of debate. Regardless of the source of the bacteria, the fact that it was found in the joint prior to implantation of a shoulder arthroplasty is concerning from the viewpoint of PJI risk. This is particularly a problem in male patients, as studies have shown a sexual dimorphism with *C. acnes* cultures, with males having a 14-fold increased risk of being colonized by the bacteria. Several centers have evaluated the possibility of the bacteria being present due to contamination from the skin edges, and it has been shown that standard skin preparation is unable to clear *C. acnes* from the skin in up to 50% of patients and is even less successful at clearing the organism from the deep dermis, with up to 73% of dermal swabs from male patients immediately following the incision culturing positive for *C. acnes*.

A recent development in shoulder surgery is the use of hydrogen peroxide to decrease the *C. acnes* load in the deep dermis sebaceous glands, with the hope that this will prevent contamination of the joint. Application of a widely commercially-available 3% topical Hydrogen peroxide in water solution *in vitro* has been found to completely eradicate *C. acnes* growth within 5 minutes and has been shown in clinical trials when used as part of the skin preparation to decrease the rate of positive cultures for *C. acnes* from 35% to 10% for deep cultures and from 34% to 17% for superficial dermal cultures. While these results show marked improvement compared to standard skin preparations, the 17% with positive dermal cultures is still concerning given the significant morbidity associated with a PJI.

Our hypothesis is that an additional application of hydrogen peroxide to the dermis itself, immediately following the skin incision, will be even more effective at eradicating this potential source of contamination deep in the joint.

## 5. Specific Aims:

Specific Aim 1: Evaluate whether the hydrogen peroxide (H2O2) applied directly to the dermal tissue after the skin incision decreases the rate of dermal swabs positive for *C. acnes*.

**Summary:** Following our standard protocols for skin preparation (which includes an application of 3% H2O2, alcohol, and then Chloraprep in sequence) and draping (with Ioban applied over the skin), we will start the procedure as normal. The skin incision will be made in standard fashion, and the knife used will be removed from the surgical field. For the experimental cohort, a lap sponge soaked in 3% H2O2 will be applied to the incision and allowed to sit for 3 minutes. Following the 3 minutes, the sponge will be removed, the wound will be flushed with 100 mL of normal saline, and the exposed dermis will be swabbed and sent for culture. In the control cohort, the dermis will be swabbed and sent for culture immediately after the skin incision is made and the knife is removed from the field.

**Hypothesis:** We hypothesize that the control cohort will show results similarly to that published in the literature, with 35-70% of the cultures positive whereas the experimental cohort will have a significantly decreased rate of positivity, close to the negative control rate, likely less than 10%.

**Specific Aim 2:** Determine if H2O2 applied to the dermal tissue after skin incision will also decrease the rate of deep cultures of capsular tissue that are positive for *C. acnes*.

**Summary:** Following the procedure summarized for specific aim 1, the surgery will be carried out in a standard fashion in both cohorts. Bone, capsule, and labral tissue from around the glenoid that is routinely excised during the surgical procedure will be collected and sent for culture as described below.

**Hypothesis:** If the H2O2 is successful at decreasing the amount of contamination present at the deep dermal tissue, the rate of deep cultures positive for *C. acnes* will also decrease, supporting the hypothesis that unexpected positive deep cultures in primary shoulder arthroplasty are likely associated with contamination from the skin edge rather than due to colonization of the arthritic joint.

## **6. Research Plan:**

**Subjects:** Once IRB approval has been obtained, up to 50 sequential male patients seen in the Hand & Upper Extremity and Sports Divisions in the Department of Orthopaedics & Rehabilitation who meet inclusion/exclusion criteria and who are boarded for primary anatomic or reverse total shoulder arthroplasty will be recruited into the study.

*Inclusion Criteria:*

- Male patients, age 40-90
- Undergoing primary anatomic or reverse total shoulder arthroplasty for glenohumeral osteoarthritis or rotator cuff arthropathy

*Exclusion Criteria:*

- Prior arthroscopic or open shoulder surgery on the ipsilateral shoulder
- Prior diagnosis of septic shoulder of the ipsilateral shoulder
- Corticosteroid injection within 3 months of the procedure
- Recently on antibiotics (within 2 weeks) prior to surgery

Assuming a rate of dermal cultures positive for *C. acnes* in the control group of 60% and a false positive rate of 10%, power analysis calculations were performed and resulted in a sample size of 13 patients per cohort needed to obtain a  $\beta = 0.2$  and an  $\alpha = 0.05$ , for a total of **26 patients**.

**Data Collection:** Under an approved HIPAA waiver, potential subjects will have their medical record and our clinical database reviewed by a member of the study staff. The following data points and information be collected for later analysis:

- Name

- Medical Record Number
- Date of Birth (to determine age)
- Gender (to determine eligibility)
- Diagnoses
- Shoulder surgical history
- Date of surgery
- Laterality
- Number of previous corticosteroid injections into the enrolled shoulder
- Past medical history of an acne breakout on the back/shoulders
- History of using prescription medications to treat acne
- Current anticoagulant or immunomodulatory medications

Additional data will be obtained during and after surgery:

- Type of implant placed (anatomic or reverse shoulder arthroplasty)
- Length of surgery
- Surgical complications
- Notes of difficulty obtaining the specified cultures
- Notes of any need to extend the skin incision during the procedure
- Postoperative wound complications

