**Methods:**

Prior to surgery, enrolled subjects will be asked to complete a short medical history questionnaire. Subjects will then be randomized 1:1 into *Experimental* or *Control* cohorts. Randomization order will be determined by using a commercial random number generator that will be made into a log that will track group assignments. Subjects will be added to the randomization log once they have received their final surgical clearance and the surgery order is determined for their surgery date. The result of the randomization will be reported by a member of the study team to the surgeon on the day of surgery prior to the start of the first procedure.

Following the standard protocol for skin preparation in shoulder arthroplasty surgery which includes an application of 3% H2O2 with gauze, isopropyl rubbing alcohol 70% USP with gauze, and then Chloraprep in sequence, and draping with Ioban applied over the skin, the procedure will start as normal.

The skin incision will be made in standard fashion, and the knife used will be removed from the surgical field. Next, for the *Experimental* cohort, a lap sponge soaked in 3% H2O2 will be applied to the incision and allowed to sit for 3 minutes. Following the 3 minutes, the sponge will be removed, the wound will be flushed with 100 mL of normal saline, any brisk bleeding will be controlled with electrocautery, and then the exposed dermis will then be swabbed and sent for culture. In the *Control* cohort, the dermis will be swabbed and sent for culture after the skin incision is made, the knife is removed from the field, and any brisk bleeding is controlled with electrocautery.

Each subject will have the following cultures taken during the procedure, using clean instruments for each culture:

1. Negative control: Before draping the patient, a culture swab will be opened on the back table and placed in the culture tube. This is essential to evaluate the false positivity rate of our lab, as other studies have reported rates of sterile, negative control cultures having a 9% positivity rate.
2. Superficial culture #1: Following control of brisk bleeding with electrocautery as noted above, the exposed dermis will be swabbed (starting at the apex of the incision and going along the entire exposed dermis in a circular pattern twice).
3. Deep culture #1: Osteophytes are routinely removed from the humeral head after dislocation of the joint. These will be crushed and sent for culture.

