### Data Safety & Monitoring Plan:

A Data and Safety Monitoring Plan (DSMP) will be implemented to ensure the safety of all participants involved in the study and to ensure the validity and integrity of the data. The Principal Investigator, with the advice and assistance of the study team, will monitor all aspects of safety. As part of standard of care, all patients undergoing shoulder arthroplasty receive wound education as part of their discharge instructions. Patients also receive continuous monitoring of their wound at post-operative Day 1 and at each clinic visit. As part of the safety monitoring program for this study, subjects will have their wound evaluated for 6 weeks post-operatively to both assure real-time participant care and unbiased monitoring of adverse outcomes. Signs of delayed wound healing, including drainage, erythema, induration, and wound dehiscence will be documented by the study team.

The Study Coordinator will meet weekly with the PI to review all events related to the study. Reports of the event will include a description of the event, a classification of seriousness, assessment of potential relationship to the study, assessment of need for change in the consent or the study activities, a summary of known prior health issues, event outcome and a classification of the main organ system involved. The classification of potential relationship to the intervention is as follows:

- **Definitely** - Temporal pattern + Known or expected AE response pattern

- **Possibly** - Temporal pattern + Known or expected AE response pattern + Could not have been produced by a number of other factors
- **Unlikely** – No Temporal pattern + Known or no AE response pattern + Could have been produced by a number of other factors
- **Definitely Not** - AE for which sufficient information exists to indicate that the cause is unrelated to the study intervention

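### The plan does not reconcile a recruitment ceiling of 50 with a calculated total of 26, or say when the arms are compared, so nothing guards against a data-dependent final sample size

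*Combined protocol and SAP*

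**What the plan says.** Section 6, Research Plan, under Subjects, says that "up to 50 sequential male patients" will be recruited. They are described as meeting the entry criteria and already booked for primary arthroplasty. After the criteria, the same text reports a power calculation that "resulted in a sample size of 13 patients per cohort needed" for β = 0.2 and α = 0.05, "for a total of 26 patients". Its inputs are positive dermal cultures "in the control group of 60% and a false positive rate of 10"%. I read the 10% as the experimental-arm rate, because Specific Aim 1 expects that arm to be "close to the negative control rate, likely less than 10"%.

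Methods sets 1:1 randomisation with a log of assignments. A study team member reports each allocation "to the surgeon on the day of surgery prior to the start of the first procedure". Cultures go to the laboratory blinded and are held for 14 days. No one else is described as blinded.

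Data Analysis names the Fisher exact test for categorical variables. It gives no time of analysis, interim look, stopping rule or adjustment of alpha. No section gives an allowance for attrition or non-evaluable patients, or a rule for ending recruitment.

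**The concern.** A reader cannot tell whether the trial is meant to randomise 26, 50 or some number between. If the report gives, say, 34 patients, nothing in the plan shows whether that number was fixed in advance or reached after results were seen.

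The conditions for an unintended data-dependent choice are present. Allocation is open to the people running the study, results arrive patient by patient, and no text restricts matching results to arms during accrual. Choosing when to stop by looking at the comparison can raise the false-positive rate and exaggerate the estimated effect.

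The stated power adds to the pressure. If 26 patients give less than the claimed 80%, a non-significant result at 26 is more likely than the plan suggests, and the ceiling leaves room to continue.

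**Working it through.** **Inputs.** From the plan: 60% v 10%, α = 0.05, power 80%, 13 per arm, ceiling 50 (25 per arm if balanced), Fisher exact test. Sidedness is not stated; I assume two-sided. Block structure is not stated; I assume balanced pairs for the exact results. Common (null) rates run from 17% to 70%. The lower end is the dermal rate that Background cites after peroxide skin preparation, which both arms receive here. The upper end is the top of the 35-70% control range in Specific Aim 1.

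**1. Reproduce the plan's 13 per arm.**
- Arcsine formula: h = 2·arcsin√0.60 − 2·arcsin√0.10 = 1.129. Then n = 2(1.960 + 0.842)²/h² = 15.70/1.274 = 12.3, rounded up to 13.
- Pooled normal formula with mean rate 0.35: n = [(1.960·√(2·0.35·0.65) + 0.842·√(0.24 + 0.09))/0.50]² = 13.04. This is 14 when rounded up; 13 per arm gives 79.9% power on this approximation.

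So 13 per arm follows from a large-sample formula without continuity correction.

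**2. Power under the planned test.** Sum the binomial probabilities of all tables with two-sided Fisher p≤0.05, at 60% v 10%:

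| Per arm | Total | Power |
|---|---|---|
| 13 | 26 | 71.0% |
| 17 | 34 | 82.7% |
| 25 | 50 | 96.0% |

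Power first reaches 80% at 17 per arm.

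**3. Type I error under optional stopping.** The joint distribution of positives in the two arms is carried forward pair by pair. At each look, tables with p≤0.05 are removed and counted as rejections.

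| Common rate | One look, 13 per arm | Two looks, 13 and 25 per arm | Every pair, 13 to 25 per arm |
|---|---|---|---|
| 17% | 1.1% | 2.8% | 5.1% |
| 30% | 2.1% | 3.7% | 6.3% |
| 50% | 2.9% | 5.2% | 7.2% |
| 60% | 2.6% | 4.7% | 6.9% |
| 70% | 2.1% | 3.7% | 6.3% |

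A single analysis at 25 per arm stays at or below 3.3% across these rates.

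*Sensitivity* (simulation, 20,000 trials per scenario). With simple randomisation, two looks give 3.8% at a rate of 17% and 5.1% to 5.6% at 35%, 60% and 70%. A look after every single patient from 26 to 50 gives about 8.6% to 10.0% at those same three rates, depending on the randomisation. At a common rate of 10%, pairwise looks give only 2.6% (exact).

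**4. Effect on the estimate.** Stopping at the first significant pairwise look, and otherwise at 25 per arm:
- At the plan's 60% v 10%, the mean estimated difference moves from 50 to 51.9 points.
- At an illustrative 34% v 10%, it moves from 24 to 26.8 points. The 34% is the dermal rate that Background cites without peroxide preparation.

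**The case against.** A reader might infer that the plan, as written, breaks the 5% level. The documents do not support that. No section schedules an interim look, a test during accrual or stopping on significance. Data Analysis describes one comparison, and the Confidentiality text, which removes identifiers once all data are collected and verified, fits analysis at the end. An unfixed total does not by itself inflate error; a decision that depends on the data must be added. That objection stands.

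A reader might also cite the Data Safety & Monitoring Plan, where "The Study Coordinator will meet weekly with the PI to review all events related to the study". The reports listed there concern adverse events: seriousness, relatedness and outcome. They are not culture results by arm, so this is no evidence of unblinded looks. The surgeon has to know the arm in order to apply the sponge, and that is not a between-arm tabulation either.

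The two numbers can also coexist, with 50 as a ceiling and 26 as the number needed. Randomisation comes after final surgical clearance, so some recruited patients may never be randomised. This is plausible, but the plan does not say it, gives no attrition allowance, and describes the 50 as already eligible. Even on this reading, the rule for ending recruitment is missing.

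Finally, the size is modest. Fisher is conservative, so the schedule that the two numbers most directly suggest (26, then 50) stays near or below 5%, and a clear excess needs many looks. The larger bias figure comes from 34% v 10%, not from the plan's own assumption. Both points stand and limit the conclusion.

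**Conclusion.** The concern holds as an unguarded risk together with an unreconciled total and power figure. It is not a finding that the trial's error rate is wrong.

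The plan leaves the final number open between 26 and 50, sets no time of comparison, and does not keep culture results by arm from those who decide on recruitment. If results were tested after each balanced pair and recruitment stopped at the first significant one, type I error would be about 5.1% to 7.2%, against 1.1% to 2.9% for one look at 13 per arm. With two balanced looks it would be about 2.8% to 5.2%. Bias in the estimate would be small under the plan's assumption (1.9 points) and somewhat larger with a weaker effect (2.8 points at 34% v 10%).

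These figures assume two-sided Fisher testing, balanced arms and stopping at p≤0.05. Access to results by arm is inferred from open allocation and laboratory-only blinding; it is not stated.

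The power point does not depend on any such behaviour: with the test the plan names, taken as two-sided, 13 per arm gives 71.0%, not 80%. The plan should be amended, because the remedy is nearly free.

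**What to change.** In Research Plan, Subjects:
- State one randomised total within the existing ceiling of 50, and say what 50 means (for example, a limit on consented patients, with the attrition it allows for).
- Restate power for that total under the Fisher test. At 60% v 10% it is 71.0% for 26, 82.7% for 34 and 96.0% for 50.

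In Data Analysis:
- State that the arms are compared once, after the 14-day cultures of the last randomised patient are final, and that no between-arm tabulation of cultures is made before then.

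The cost is a few sentences and no patients beyond the stated ceiling. The team gives up the option of stopping early after seeing results, and if it keeps 26, the stated power becomes less favourable.

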#### Data Analysis:

Descriptive statistics will be used to describe both the experimental and control cohort's demographic characteristics. The two cohorts' demographics and culture results will then be compared for differences with use of standard statistical tests appropriate for the data and study results. The Student T-test will be used for continuous variables and the Fisher Exact test will be used for the categorical variables. Univariate analysis will be performed between the two groups given the small number of patients in each group and the randomized design of this study.

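### The 13-per-cohort sample size names no test and no sidedness; with the planned Fisher exact test taken two-sided at 0.05, power at 60% versus 10% is 71%, not 80%

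*Combined protocol and SAP*

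**What the plan says.** All references are to the combined protocol and SAP.

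- **Section 6, Research Plan, Subjects.** The calculation assumes a rate of positive dermal cultures "in the control group of 60% and a false positive rate of 10" per cent. It "resulted in a sample size of 13 patients per cohort needed to obtain a" beta of 0.2 with alpha 0.05, and gives the total as 26. No test, formula, software or sidedness is stated. The same section allows recruitment of "up to 50 sequential male patients" without relating 50 to 26.
- **Data Analysis.** Demographics and "culture results will then be compared for differences", and "the Fisher Exact test will be used for the categorical variables". Sidedness is again not given.
- **Section 5, Specific Aim 1.** The aim is directional: whether the intervention "decreases the rate of dermal swabs positive for" *C. acnes*. The hypothesis puts the experimental cohort "close to the negative control rate, likely less than 10" per cent.

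**The concern.** A sample size carries its stated power only for the test that will be used. Fisher's exact test is conservative in small samples, so a number obtained from a normal approximation, or from a one-sided calculation, can fall short when the data are analysed with a two-sided Fisher test.

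The text does not settle which is meant. Comparing groups for differences is conventionally two-sided, whereas Aim 1 asks about a decrease. Two things are at stake. On the two-sided reading, the risk of missing an effect of exactly the planned size is higher than the protocol states. And if sidedness is chosen only once the data are in, some results could be called positive or negative according to that choice.

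**Working it through.** **Inputs.** Control rate 0.60, second rate 0.10, alpha 0.05, beta 0.2 and 13 per cohort (section 6, Subjects); 1:1 allocation (Methods); Fisher exact test (Data Analysis). The protocol labels the 10% a false positive rate. I read it as the experimental-cohort rate because Aim 1 expects that cohort to be near the negative-control rate and no other second proportion is given.

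**Step 1: can 13 be reproduced?** Yes, in more than one way.

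- Two-sided pooled normal approximation, with mean rate 0.35:
  n = [1.960 × √(2 × 0.35 × 0.65) + 0.842 × √(0.60 × 0.40 + 0.10 × 0.90)]² / 0.50²
  = (1.322 + 0.483)² / 0.25 = 13.04.
  Strict rounding up gives 14; approximate power at 13 is 79.9%.
- Two-sided arcsine formula: 12.3, rounded up to 13.
- One-sided exact Fisher test at 0.05: 79.1% at 12 and 81.3% at 13, so 13 is the first size above 80%.

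The figure is therefore not an arithmetic slip, but its origin cannot be determined from the document.

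**Step 2: exact power of the planned test at 13 per cohort.** Power is the sum, over all pairs of counts with p ≤ 0.05, of Binomial(13, 0.60) × Binomial(13, 0.10). The table groups it by the number of experimental positives.

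| Experimental positives | Probability | Control positives needed, two-sided (probability) | Control positives needed, one-sided (probability) |
|---|---|---|---|
| 0 | 0.2542 | 5 or more (0.9679) | 4 or more (0.9922) |
| 1 | 0.3672 | 7 or more (0.7712) | 6 or more (0.9023) |
| 2 | 0.2448 | 8 or more (0.5744) | 7 or more (0.7712) |
| 3 | 0.0997 | 9 or more (0.3530) | 9 or more (0.3530) |
| 4 | 0.0277 | 10 or more (0.1686) | 10 or more (0.1686) |
| 5 | 0.0055 | 11 or more (0.0579) | 11 or more (0.0579) |

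Higher experimental counts add a negligible amount.

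- Two-sided: 0.2460 + 0.2832 + 0.1406 + 0.0352 + 0.0047 + 0.0003 = **0.710**
- One-sided: 0.2522 + 0.3313 + 0.1888 + 0.0352 + 0.0047 + 0.0003 = **0.8125**

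**Step 3: size needed if two-sided.** Two-sided Fisher power at 60% versus 10%:

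| Per cohort | 12 | 13 | 14 | 15 | 16 | 17 | 25 |
|---|---|---|---|---|---|---|---|
| Power | 63.9% | 71.0% | 74.2% | 73.9% | 78.6% | 82.7% | 96.0% |

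Seventeen per cohort (34 in total) is the first size above 80%, and power stays above 80% at every size from 17 to 25.

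**Step 4: results whose conclusion depends on sidedness, 13 per cohort.**

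| Control v experimental positives | One-sided p | Two-sided p | Probability at 60% v 10% |
|---|---|---|---|
| 4 v 0 | 0.048 | 0.096 | 0.0062 |
| 6 v 1 | 0.037 | 0.073 | 0.0482 |
| 7 v 2 | 0.048 | 0.097 | 0.0482 |

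The sum is about 0.103, which accounts for the whole gap 0.8125 − 0.7100.

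**Step 5: sensitivity to the rates, two-sided Fisher, 13 per cohort.** With control at 60%, power is 71.0% at an experimental rate of 10%, 73.6% at 9% and 84.0% at 5%. With the experimental rate at 10%, power is 19% at a control rate of 35%, 49% at 50% and 88% at 70%.

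**Step 6: type I error.** At 13 per cohort the maximum size is 2.9% for the two-sided Fisher test and 2.4% for the one-sided test, so neither exceeds 5%.

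**The case against.** The strongest reply is that nothing was miscalculated. Thirteen follows from ordinary methods, and the 71% arises only if the Fisher test is two-sided. That is right, and the point is put conditionally. But the approximations that yield 13 are not the planned analysis, and with the planned test the stated beta holds only one-sided.

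Second, the 10% is labelled a false positive rate, and Aim 1 expects the experimental rate to be "likely less than 10" per cent. At a 60% control rate, 71.0% is then the low end: two-sided power is 78.8% at an experimental rate of 7% and 81.4% at 6%. This stands as a qualification. Still, 10% is the figure the calculation uses, and Methods cites 9% positivity even for sterile control swabs.

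Third, 34 patients fit under the ceiling of 50, and 25 per cohort gives 96.0%. This softens the problem but does not remove it: 26 is the stated requirement, and a trial that stops there complies with the protocol.

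Fourth, the control rate matters more than this gap. Aim 1 expects 35–70%, a range over which two-sided power at 13 runs from 19% to 88%. That is true, and a reason to show the dependence on the rates when the power is restated. It does not make the stated 80% correct at the protocol's own planning values.

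**Conclusion.** The point holds. Neither the sample-size paragraph nor Data Analysis gives sidedness, and the sample-size paragraph names no method. If the Fisher test is two-sided at 0.05, power at 13 per cohort is 71.0%, nine points below the stated 80%: the chance of missing the planned effect is 29% rather than 20%, and 17 per cohort would be needed. If it is one-sided at 0.05, power is 81.3% and the statement is correct.

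This rests on reading 10% as the experimental-cohort rate, on exactly 13 evaluable patients per cohort, and on enrolment ending at 26. It concerns the stated power and an unmade choice that would settle the conclusion in about one trial in ten at the planning rates. It is not a threat to type I error, provided the choice is made before the data are seen. It should be fixed.

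**What to change.** Before any results are examined, state the test, its sidedness and alpha in both the sample-size paragraph and Data Analysis, and say that 10% is the assumed experimental-cohort rate.

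- **If two-sided Fisher is intended**, restate the power, for example: *Dermal culture positivity will be compared with a two-sided Fisher exact test at alpha = 0.05; with 13 patients per cohort and rates of 60% versus 10%, power is about 71%.* A further clause giving power at other control rates (49% at 50%, 88% at 70%) would show how far the figure depends on that assumption.
- **If a one-sided test at 0.05 is intended**, say so in both places; 13 per cohort then gives 81.3%.

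The cost is one sentence in each of two paragraphs, with no added patients, procedures or data. On the two-sided reading, the price is a less favourable stated power.

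Two alternatives are optional. One is to name 34 patients as the single final number: 8 more than 26, and within the ceiling of 50. The other is to pre-specify a two-sided Boschloo test ordered on the two-sided Fisher p-value. At 13 per cohort its cut-off must be about 0.097, so that 7 v 2 (p = 0.09684) is included; maximum size is then 4.85% and power 81.3%. The ordering rule must be written out, because a cut-off of 0.0968 taken literally drops that table and lowers power to 76.4%.
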